#### **6.6.1** Safety Review Committee

A Safety Review Committee (SRC), comprised of the PI, a medical expert with experience in vaccine pharmacovigilance not involved with the study, the Emmes medical monitor, SIIPL and PATH medical officer will monitor safety throughout the duration of the study. The Emmes study statistician with assistance of the data management staff will prepare safety reports as needed for SRC discussions. During the vaccination period, the SRC will review weekly safety data. At any time during the study, the Emmes Coordinating Center will notify the SRC of ad hoc review if pause criteria may have been met. The SRC reviews will be summarized with consensus recommendations to the study Sponsor as to whether there are safety concerns and whether the study should continue without change, be modified, or be stopped. The SRC may request review of unblinded safety data by the pharmacovigilance expert in its deliberation. SRC consensus recommendations regarding modifying or stopping further enrolment may involve Sponsor consultation with the local regulatory authority.

#### 6.6.2 Study Pause Rule

The following study pause rules will automatically pause or halt further vaccinations. However participants already enrolled will continue to be followed for safety during the pause. These pause rules refer to suspected adverse reactions and will be triggered automatically if any of the events described below are met during the conduct of the study:

- One or more participants experience a serious adverse reaction.
- One or more participants experience a Grade 4 injection site reaction.
- Two or more participants experience the same Grade 3 injection site reaction.
- Two or more participants experience the same severe (Grade 3) systemic reactogenicity signs or symptoms, within seven days following vaccination.
- Two or more participants experience the same vaccine-related Grade 3 or higher clinical (including fever) or laboratory abnormality.

#### 6.7 Multicenter Studies

This is a single site study.

#### 6.8 Multiple Comparisons/Multiplicity

This is a FIH study so the primary purpose of statistical comparisons is to screen out potential solicited reactogenicity events that need further clinical evaluation. Therefore, the statistical analyses are not considered formal statistical hypothesis tests and it is acknowledged that there will be inflated Type I errors (i.e., inflated false statistical significances) from performing multiple unadjusted comparisons.

#### 7 STUDY PARTICIPANTS

#### 7.1 Participant Disposition

Screened participants who were ineligible for enrollment in the study will be summarized by inclusion and exclusion criteria and other reasons for ineligibility (Table 14.1.1). The composition of analysis populations, including reasons for participant exclusion, by treatment group, is presented in Table 14.1.2.

The disposition of participants in the study will be tabulated by treatment group and overall (Table 14.1.3). This table will show the number of participants screened, enrolled, received vaccination, completed Visit 4 (Day 29), completed follow-up, and in PP population.

A flowchart presenting the disposition of study participants, adapted from the CONSORT statement [32] will be included (Figure 14.1.1). The flowchart includes the number of participants eligible, enrolled and randomized, lost to follow-up, and analyzed, by treatment group.

A listing of participants who discontinued or terminated early from the study and who were excluded from the FA population and the PP population will be included in Listings 16.2.1 and 16.2.3, respectively.

#### 7.2 Protocol Deviations

A summary of protocol deviations will be presented by the deviation category, reason, and treatment group in Table 10.2.1. This table will provide both the number of participants and the number of deviations for each category and treatment group.

All participant-specific protocol deviations and non-participant-specific protocol deviations will be included as data listings (Listings 16.2.2.1 and 16.2.2.2, respectively).

TABLE 10.2.1: Distribution of Protocol Deviations by Category, Reason, and Treatment Group

		Adjuvanted MCV-5 (N=X)		Non- adjuvanted MCV-5 (N=X)		Menactra® (N=X)		All Participants (N=X)	
Category	Deviation Reason	# of Parti.	# of Dev.	# of Parti.	# of Dev.	# of Parti.	# of Dev.	# of Parti.	# of Dev.
	Any type	х	Х	х	Х	X	х	Х	Х
	Participant illness	Х	X	X	X	X	х	X	Х
	Unable to comply	X	X	X	X	X	х	X	X
	Participant refusal	X	X	X	X	X	х	X	X
Eligibility/enrollment	Clinic error	х	Х	х	X	X	х	Х	X
	Pharmacy error	х	X	х	X	x	х	х	x
	Laboratory error	х	х	х	Х	X	х	х	X
	Investigator/study decision	х	Х	х	Х	X	х	х	x
	Other	х	X	Х	X	X	х	Х	X
	Any type	Х	X	Х	X	X	х	Х	X
	Participant illness	Х	X	Х	X	X	х	Х	X
	Unable to comply	х	X	х	х	х	х	х	X
	Participant refusal	х	Х	Х	X	X	х	Х	X
Product administration schedule	Clinic error	Х	X	Х	X	X	х	Х	X
Schedule	Pharmacy error	х	Х	Х	X	X	х	Х	X
	Laboratory error	Х	X	Х	X	Х	х	Х	Х
	Investigator/study decision	х	Х	Х	X	X	х	Х	X
	Other	х	X	Х	X	X	х	Х	X
	Any type	х	Х	Х	X	X	х	Х	X
	Participant illness	Х	X	Х	X	Х	х	Х	Х
	Unable to comply	х	X	Х	X	Х	х	х	Х
	Participant refusal	х	Х	х	X	Х	Х	х	Х
Follow-up visit schedule	Clinic error	х	X	Х	X	Х	х	х	X
Schedule	Pharmacy error	х	Х	х	X	Х	Х	х	Х
	Laboratory error	х	X	х	X	Х	Х	х	Х
	Investigator/study decision	х	X	Х	X	Х	х	х	Х
	Other	х	X	Х	X	X	X	х	X

TABLE 10.2.1:
Distribution of Protocol Deviations by Category, Reason, and Treatment Group (continued)

		Adjuvanted MCV-5 (N=X)		Non- adjuvanted MCV-5 (N=X)		Menactra® (N=X)		All Participants (N=X)	
Category	Deviation Reason	# of Parti.	# of Dev.	# of Parti.	# of Dev.	# of Parti.	# of Dev.	# of Parti.	# of Dev.
	Any type	х	х	X	х	X	х	Х	X
	Participant illness	Х	Х	х	Х	Х	х	Х	X
	Unable to comply	х	х	X	Х	X	х	X	X
	Participant refusal	х	Х	х	Х	х	х	X	X
Protocol procedure / assessment	Clinic error	х	Х	х	х	х	х	х	Х
ussessment	Pharmacy error	х	х	X	х	х	х	х	X
	Laboratory error	х	х	X	х	Х	Х	Х	X
	Investigator/study decision	х	х	Х	X	Х	х	Х	X
	Other	х	х	Х	х	Х	х	Х	X
	Any type	х	х	Х	х	Х	Х	Х	X
	Participant illness	х	х	х	х	Х	х	Х	X
	Unable to comply	х	х	х	х	Х	х	Х	X
	Participant refusal	х	х	х	х	Х	х	Х	X
Product administration	Clinic error	х	х	х	х	Х	х	Х	X
daministration	Pharmacy error	х	х	х	х	Х	х	Х	X
	Laboratory error	х	х	Х	х	Х	х	Х	X
	Investigator/study decision	х	х	Х	х	Х	х	Х	X
	Other	х	х	х	х	Х	х	Х	X
	Any type	х	х	х	х	Х	х	Х	X
	Participant illness	х	х	Х	х	Х	х	Х	X
	Unable to comply	Х	х	Х	Х	Х	х	Х	X
	Participant refusal	х	х	х	х	х	х	х	X
Blinding policy / procedure	Clinic error	х	х	х	X	х	Х	Х	Х
procedure	Pharmacy error	х	х	х	X	х	Х	Х	Х
	Laboratory error	х	х	х	х	х	х	х	X
	Investigator/study decision	х	Х	х	X	х	X	Х	Х
	Other	х	х	х	х	х	х	х	Х

[Implementation: Only include the Deviation categories and reasons reported in the study.]

#### 8 IMMUNOGENICITY EVALUATION

The secondary and exploratory immunogenicity outcomes for the study are based on the rSBA titer for Meningococcal serogroup A, C, Y, W and X specific antibodies. For each participant, the rSBA titer will be measured at Day 1 prior to vaccination and at Day 29 (28 days post vaccination). All immunogenicity analyses will be conducted using the PP population and FA population. Individual participant data listings of immunogenicity will be presented in Listing 16.2.6.

Due to the hypothesis generating nature of multiple statistical comparisons for immunogenicity associated with multiple endpoints for this early phase FIH study, all estimations will be carried out using a two-sided 5% Type I error rate without an adjustment for multiple comparisons.

#### 8.1 Secondary Endpoint - a 4-fold response in rSBA titer

The percentage of participants with a 4-fold response in rSBA titer against serogroups A, C, W, Y and X will be defined as follows:

- For participants with a pre-vaccination rSBA < 8, a post-vaccination titer >= 32.
- For participants with a pre-vaccination rSBA titer ≥ 8, a post-vaccination rSBA titer of at least 4 times the pre-vaccination titer.

The number and percentage of participants with a 4-fold response in rSBA titer will be summarized at Day 29, along with two-sided 95% exact confidence intervals (CIs) for each of the proportions. Two-sided exact 95% CIs for the three pair-wise proportion differences between the three treatment groups will be computed using the unconditional exact method proposed by Chan and Zhang (1999).(Note: In SAS, this is the RISKDIFF(METHOD=FMSCORE) option in PROC FREQ).

Table 14.2.1.1 will summarize the number and percentage of participants with a 4-fold response in rSBA titer for each of the five serogroups and 95% CIs for each treatment group and treatment group comparison. CIs will be visualized graphically in Forest plots as depicted in Figure 14.2.1.2.

#### 8.2 Secondary Endpoint - percentages of participants with rSBA titer ≥ cut-off

The number and percentages of participants with rSBA titer  $\geq 8$  and  $\geq 128$  for each of the five serogroups will be summarized at Day 1 and Day 29, along with two-sided 95% exact confidence intervals (CIs) for each of the proportions. Two-sided exact 95% CIs for the three pair-wise proportion differences between the three treatment groups will be computed using the unconditional exact method proposed by Chan and Zhang (1999).(Note: In SAS, this is the RISKDIFF(METHOD=FMSCORE) option in PROC FREQ).

Table 14.2.2.1 will summarize the number and percentages of participants with rSBA titer  $\geq 8$  and  $\geq 128$  for each of the five serogroups and 95% CIs for each treatment group and treatment group comparison at Day 1 and Day 29. CIs will be visualized graphically in Forest plots as depicted in Figure 14.2.2.2.

#### 8.3 Secondary Endpoint - Geometric Mean Titers

The number of observations, geometric mean titer (GMT) and geometric 95% confidence interval will be reported. For rSBA titers below the assay detection of 8, an arbitrary value of half of the assay's cut-off (or 4) will be used. The GMT for each of the 5 serogroups will be calculated as the exponentiation of the mean of the natural logarithms of the rSBA titer. The two-sided 95% confidence intervals of GMTs for serogroups A, C, W, Y, and X will be calculated by exponentiating the lower and upper limits of the 95% CIs of the natural logarithms of the rSBA titer. The computation of the 95% CIs of the natural logarithms of the rSBA titer will be based on the t-distribution. Two-sided 95% CIs for the ratios of GMTs between treatment groups will be constructed using the log normal distribution. The log values will be used to construct a CI using the t-distribution for the mean difference between three pair-wise treatment groups. The mean difference and the corresponding CI limits will then be exponentiated to obtain the GMT ratio and the corresponding CI. If the values deviate from the log normal distribution, a non-parametric method may be used for the analysis of the GMT.

Table 14.2.3.1 will summarize the GMTs and 95% CIs per serogroup for each treatment group and treatment group comparison at Day 1 and Day 29. CIs will be visualized graphically in Forest plots as depicted in Figure 14.2.3.2.

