#### **6.3.3** Per Protocol Population

All participants in the FA population who are assigned the study vaccination with no major protocol violations that are determined to potentially interfere with the immunogenicity assessment of the study vaccine and who have at least one immunogenicity assessment will be included in the Per Protocol (PP) population. This population will serve as the primary analysis population for the immunogenicity endpoints.

The criteria for exclusion of participants from the PP population will be established before breaking the blind and will be based on the blinded review of protocol violations.

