### **TABLE 14.2.2.1(d):**

Secondary Analysis of Percentages of Participants with rSBA Titers ≥128, by serogroup – Full Analysis Population
As above.

TABLE 14.2.3.1(a): Secondary Analysis of rSBA Geometric Mean Titers per Serogroup - Per Protocol Population

				M	eningococcal	Polysacchari	de			
Treatment Group	1	A	(	С	,	Y	•	W		X
(Number of Participants)	GMT	95% CI	GMT	95% CI	GMT	95% CI	GMT	95% CI	GMT	95% CI
Day 1 (Baseline)										
Adjuvanted MCV-5 (N=XX)										
Non-adjuvanted MCV-5 (N=XX)										
Menactra® (N=XX)										
Treatment Group Comparisons	Ratio	95% CI	Ratio	95% CI	Ratio	95% CI	Ratio	95% CI	Ratio	95% CI
Adjuvanted MCV-5 vs Non-Adjuvanted MCV-5										
Adjuvanted MCV-5 vs Menactra®										
Non-Adjuvanted MCV-5 vs Menactra®										
Day 29										
Adjuvanted MCV-5 (N=XX)										
Non-adjuvanted MCV-5 (N=XX)										
Menactra® (N=XX)										
Treatment Group Comparisons	Ratio	95% CI	Ratio	95% CI	Ratio	95% CI	Ratio	95% CI	Ratio	95% CI
Adjuvanted MCV-5 vs Non-Adjuvanted MCV-5										
Adjuvanted MCV-5 vs Menactra®										
Non-Adjuvanted MCV-5 vs Menactra®										
Fold-Rise From Baseline	GMFR	95% CI	GMFR	95% CI	GMFR	95% CI	GMFR	95% CI	GMFR	95% CI
Adjuvanted MCV-5										
Non-adjuvanted MCV-5										
Menactra ®		_			_	_				_

[figure not shown]
GMT = Geometric Mean Titer; CI = Confidence Interval; GMFR = Geometric Mean Fold Rise; Ratio = Ratio of GMT.

TABLE 14.2.3.1(b): Secondary Analysis of rSBA Geometric Mean Titers per Serogroup - Full Analysis Population

				M	eningococcal	Polysacchari	de			
Treatment Group	1	A	(	С	`	Y	•	W		X
(Number of Participants)	GMT	95% CI	GMT	95% CI	GMT	95% CI	GMT	95% CI	GMT	95% CI
Day 1 (Baseline)										
Adjuvanted MCV-5 (N=XX)										
Non-adjuvanted MCV-5 (N=XX)										
Menactra® (N=XX)										
Treatment Group Comparisons	Ratio	95% CI	Ratio	95% CI	Ratio	95% CI	Ratio	95% CI	Ratio	95% CI
Adjuvanted MCV-5 vs Non-Adjuvanted MCV-5										
Adjuvanted MCV-5 vs Menactra®										
Non-Adjuvanted MCV-5 vs Menactra®										
Day 29										
Adjuvanted MCV-5 (N=XX)										
Non-adjuvanted MCV-5 (N=XX)										
Menactra® (N=XX)										
Treatment Group Comparisons	Ratio	95% CI	Ratio	95% CI	Ratio	95% CI	Ratio	95% CI	Ratio	95% CI
Adjuvanted MCV-5 vs Non-Adjuvanted MCV-5										
Adjuvanted MCV-5 vs Menactra®										
Non-Adjuvanted MCV-5 vs Menactra®										
Fold-Rise From Baseline	GMFR	95% CI	GMFR	95% CI	GMFR	95% CI	GMFR	95% CI	GMFR	95% CI
Adjuvanted MCV-5										

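### The Day 29 GMT-ratio intervals are valid but take no account of the Day 1 titer; a supportive baseline-adjusted ratio, fixed before the interim analysis, is a cheap, low-urgency gain

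*SAP*

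**What the plan says.** SAP 8.3 and protocol 7.5.2 form each GMT ratio by exponentiating a difference of mean log titers between two arms, with a t-based interval: "The log values will be used to construct a CI using the t-distribution for the mean difference between three pair-wise treatment groups". Titers below 8 are set to 4. SAP 8.3 also leaves a way out: "If the values deviate from the log normal distribution, a non-parametric method may be used for the analysis of the GMT".

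SAP section 8 schedules an rSBA titer for each participant on Day 1 before vaccination and again on Day 29, and adds: "All immunogenicity analyses will be conducted using the PP population and FA population". The per-protocol (PP) set is primary for immunogenicity (SAP 6.3.3). It takes participants without major violations "who have at least one immunogenicity assessment will be included in the Per Protocol (PP) population", so a Day 1 titer is not guaranteed.

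The Day 1 titer is used in three places:
- Seroconversion: for a Day 1 titer of 8 or more, SAP 8.1 requires "a post-vaccination rSBA titer of at least 4 times the pre-vaccination titer". This yes/no response is compared between arms.
- Table 14.2.3.1 prints Day 1 GMTs and their pair-wise ratios.
- The same table has a block headed "Fold-Rise From Baseline", with a geometric mean fold rise (GMFR) and interval for each arm but no between-arm row. The footnote of part (b) defines an abbreviation for a difference in GMFR that no row uses.

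SAP 6.4 states that there is no prior plan for covariates.

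**The concern.** Protocol 2.4.1 and SAP 4.1 want the immunogenicity data to show differences between the two formulations and against the reference vaccine. The GMT ratios are the planned contrasts of titer level, with 20 participants per arm. At that size a chance Day 1 difference in some comparison is likely. If Day 1 and Day 29 titers are correlated, part of that difference carries into the Day 29 ratio. The tables let a reader see the Day 1 gap, but no between-arm interval for the Day 29 level accounts for it.

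At stake is some precision, and how a Day 29 ratio is read when the arms began unequal. Pre-specification has a deadline. SAP 6.6 gives the sponsor unblinded safety data by arm at the interim analysis, together with immunogenicity data for the first 30 participants. An adjustment chosen after that could be called selective.

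**Working it through.** **Inputs from the documents.** 20 per arm; two-sided 95% intervals without multiplicity adjustment (SAP 8); titers below 8 set to 4. The plan states no precision figure for GMT ratios, so there is none to reproduce.

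**Assumed inputs.** Two-fold dilutions; log2 SD 2.5, that is ln SD 2.5 × 0.693 = 1.73; 20% to 95% of Day 1 titers below 8; a range of correlations. The correlations below are latent, meaning before titers are rounded to dilutions and floored at 4.

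**Planned interval.** Half-width on the ln scale = t(0.975, 38) × SD × √(2/20) = 2.0244 × 1.73 × 0.3162 = 1.11. The limits are the ratio times or divided by e^1.11 = 3.03.

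**ANCOVA, closed form.** With r the correlation of the measured log titers, the expected half-width relative to plan is (2.0262/2.0244) × √(1 + 1/36) × √(1 − r²) = 1.0147 × √(1 − r²). At r = 0 this is 1.015. Break-even is √(1 − 1/1.0147²) = 0.17.

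**ANCOVA, simulation with flooring** (200,000 pairs of arms per setting; mean half-width divided by the planned one):

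| Latent correlation | 20% below 8 | 50% | 80% | 90% | 95% |
|---|---|---|---|---|---|
| 0 | 1.014 | 1.014 | 1.014 | 1.014 | 1.012 |
| 0.2 | 0.996 | 0.999 | 1.005 | 1.007 | 1.008 |
| 0.3 | 0.971 | 0.979 | 0.992 | 1.000 | 1.003 |
| 0.5 | 0.890 | 0.912 | 0.952 | 0.973 | 0.987 |
| 0.6 | 0.829 | 0.863 | 0.923 | 0.955 | 0.975 |

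At latent 0.5 the factor 3.03 becomes 3.03^0.890 = 2.68 at best and 3.03^0.987 = 2.99 at worst.

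**Latent against measured.** Flooring lowers the correlation that the data will show. Latent 0.5 is a measured 0.44, 0.28 and 0.22 at 50%, 90% and 95% below 8. The closed form then gives 1.0147 × √(1 − 0.44²) = 0.911, and likewise 0.974 and 0.990, close to the table. Break-even rises from about 0.17 to 0.35 on the latent scale but stays near 0.17 for measured titers.

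**Coverage.** Over all simulated pairs both methods cover 95%. A Day 1 gap above 0.5 SD occurs in about 12% of pairs (11% at 90% below 8, 5% at 95%). In those pairs the unadjusted interval covers 92–94%, 87–93% and 84–91% at latent 0.3, 0.5 and 0.6, against about 95% for ANCOVA. The proposed contrasts number 4 serogroups × 3 pairs + 1 for X = 13. The expected number with such a gap is 13 × 0.12 = 1.6, 13 × 0.11 = 1.4 or 13 × 0.05 = 0.7.

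**Sparse Day 1 data.** Among the 40 participants of a pair, the chance that only one or two have a detectable Day 1 titer is 21% at 90% below 8 and 55% at 95% (binomial). The chance that none has is 0.90^40 = 1.5% and 0.95^40 = 13%.

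**Serogroup X.** Menactra contains no X antigen, so a common slope for X against Menactra is not credible.

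**The case against.** The strongest reply is that nothing is broken. The endpoint is the GMT at 28 days, and the planned ratio estimates it directly. Immunogenicity is secondary, descriptive and unpowered (SAP 2.1 and section 5). Protocol 2.3 leaves the choice of formulation to a later Phase 2 trial. SAP 6.4 declines covariates openly. All of this stands, and it is why the urgency is low.

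A reader might infer that the intervals are wrong because they ignore Day 1. The documents do not support that: arms are randomized and coverage is 95% overall. The shortfall above is conditional on a large Day 1 gap and on an assumed correlation.

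A reader might also infer that the plan offers no baseline-corrected comparison at all. That goes too far. Among participants with both titers, the Day 29 ratio divided by the Day 1 ratio equals the ratio of the two fold rises, a corrected point estimate with the slope fixed at 1. Table 14.2.3.1 supplies the parts. Seroconversion uses Day 1 with pair-wise exact intervals, and Listing 16.2.6 gives every titer. Missing are an interval for the corrected ratio and a slope taken from the data. Fixing the slope at 1 can cost width: in a simulation with half the Day 1 titers below 8, that interval was 20% wider than planned at latent correlation 0 and 4.5% wider at 0.3. The listing permits a later ANCOVA, but not a pre-specified one.

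Finally, heavy flooring can leave the slope resting on one or two people. That stands, and it limits what the adjusted row can show.

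**Conclusion.** The plan's intervals are valid, and no planned between-arm interval for the Day 29 titer level uses the Day 1 titer. A supportive adjusted ratio would be a cheap gain in precision and interpretation, of low urgency.

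Its size rests wholly on assumptions: 20 per arm with both titers, two-fold dilutions, and 20% to 95% of Day 1 titers below 8. Intervals would be about 1% to 11% narrower at latent correlation 0.5, about 3% narrower to 0.3% wider at 0.3, and up to 1.4% wider at 0. A sure gain is another tempting inference that the documents do not support. They give no correlation, and SAP 4.3.2 excludes prior meningococcal vaccination and known exposure, so many Day 1 titers may be below 8. The gain could then be small or nil.

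**What to change.** Before the interim analysis of SAP 6.6, add one paragraph to SAP 8.3 and name the covariate in SAP 6.4:

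- A supportive pair-wise ANCOVA of ln(Day 29 titer) on treatment and ln(Day 1 titer) with a common slope, at the final analysis, in the PP population and repeated in the full analysis population.
- All three pairs for A, C, Y and W. For X, adjuvanted against non-adjuvanted MCV-5 only; X against Menactra stays unadjusted.
- Participants with both titers, the same rule of 4 for titers below 8, and n shown.
- Adjusted ratio and 95% CI beside the unadjusted ratio in Table 14.2.3.1. The unadjusted ratio leads and both are reported. If they differ, describe the Day 1 gap next to them.
- The unadjusted ratio only, if all Day 1 titers in a pair are below 8 or if the non-parametric option is used.
- Remove the unused footnote on the difference in GMFR from Table 14.2.3.1(b), or give it a row.

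The cost is a paragraph, some table rows and a few lines of code, with no new data. Each pair spends one degree of freedom, and the adjusted interval is up to 1.4% wider if the titers are uncorrelated. Participants without a Day 1 titer drop out of the adjusted model only. A descriptive table gains 13 × 2 = 26 intervals without multiplicity adjustment.

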#### 9 SAFETY EVALUATION

#### 9.1 Demographic and Other Baseline Characteristics

Summaries of sex, ethnicity, and race will be presented by treatment group and overall in Table 14.1.4.1 for all participants in the FA population. Ethnicity will be categorized as Hispanic or Latino, or not Hispanic and not Latino. In accordance with NIH reporting policy, participants may self-designate as belonging to more than one race or may refuse to identify a race, the latter reflected in the CRF as "No" to each racial option. Participants belonging to more than one race will be categorized as multi-racial and participants refusing to identify with a race will be classified as unknown on the table. Age will be summarized in years by treatment group and overall in Table 14.1.4.2.

Individual participant listings will be presented for all demographic characteristics (Listing 16.2.4.1).

